4.2. Overall Study Duration

Individual participants will participate for a duration of up to 21 weeks (4 weeks screening, 12 weeks treatment, 4-5 weeks safety follow-up; see [Figure 1](#)).

The study begins when the first participant signs the ICF. The end of the study is defined as the date of the last visit of the last participant in the study.

A participant is considered to have completed the study if he/she has completed all study visits, including the follow-up visit.

The investigator will be expected to monitor for and report any SAEs, AEs of special interest, and pregnancies as detailed in [Section 9](#). The remaining participants are considered to be on study until a discontinuation criterion is met and written notification is provided to the sponsor.

4.3. Study Termination

The investigator retains the right to terminate study participation at any time, according to the terms specified in the study contract. The investigator is to notify the IRB/IEC in writing of the study's completion or early termination, send a copy of the notification to the sponsor or sponsor's designee, and retain 1 copy for the site study regulatory file.

The sponsor may terminate the study electively, or if required by regulatory agency. If the study is terminated prematurely, the sponsor or designee will notify the investigators, the IRBs and IECs, and regulatory bodies of the decision and reason for termination of the study.

5. STUDY POPULATION

Deviations from eligibility criteria are not allowed because they can potentially jeopardize the scientific integrity of the study, regulatory acceptability, and/or participant safety. Therefore, adherence to the criteria as specified in the Protocol is essential. Prospective approval of Protocol deviations to recruitment and enrollment criteria, also known as Protocol waivers or exemptions, are not permitted.

5.1. Inclusion Criteria

Participants are eligible to be included in the study only if all of the following criteria apply:

1. Ability to comprehend and willingness to sign a written ICF for the study.
2. Age \geq 18 years at the time of signing the ICF.
3. Primary SS diagnosed according to the revised AECG criteria ([Vitali et al 2002](#)), defined as presence of any 4 of the 6 items below, with at least items d) and f), or the presence of any 3 of items c), d), e) and f):
 - a. Ocular dryness symptoms.
 - b. Oral dryness symptoms.
 - c. Schirmer's test \leq 5 mm/5 min.
 - d. Focus score \geq 1 focus/4 mm² on minor salivary gland biopsy.
 - e. Unstimulated whole salivary flow \leq 0.1 mL/min.
[REDACTED]
4. Minimum score of 2 on the SGUS score for parotid and submandibular glands.
5. ESSDAI score \geq 5.
[REDACTED]
7. Symptomatic oral dryness score of at least 5 on patient questionnaire.
8. Willingness to avoid pregnancy or fathering children based on the criteria below:
 - a. Woman of nonchildbearing potential (ie, surgically sterile with a hysterectomy and/or bilateral oophorectomy OR \geq 12 months of amenorrhea and at least 50 years of age, and FSH levels $>$ 30 IU/L).
 - b. Woman of childbearing potential who has a negative serum pregnancy test at screening and negative urine pregnancy test before the first dose on Day 1 and who agrees to take appropriate precautions to avoid pregnancy (with at least 99% certainty) from screening through safety follow-up visit. Permitted methods that are at least 99% effective in preventing pregnancy (see [Appendix A](#)) should be communicated to the participant and her understanding confirmed.
 - c. Man who agrees to take appropriate precautions to avoid fathering children (with at least 99% certainty) or from sperm donation from screening through 93 days after treatment with INCB050465. Permitted methods that are at least 99% effective in preventing pregnancy (see [Appendix A](#)) should be communicated to the participant and his understanding confirmed.

5.2. Exclusion Criteria

Participants are excluded from the study if any of the following criteria apply:

1. Diagnosis of secondary SS according to the revised AECG criteria (eg, the presence of a previously diagnosed or a present diagnosis of RA, SLE, systemic sclerosis, mixed connective tissue disease, polymyositis, dermatomyositis, immunoglobulin G4-related disorder, sarcoidosis, or any other defined autoimmune rheumatologic disorder).
 - a. NOTE: Nonrheumatologic autoimmune disorders (eg, Hashimoto thyroiditis, alopecia, vitiligo, Type 1 diabetes mellitus) do not constitute an exclusion; the medical monitor should be consulted if there are questions regarding a specific participant's disease history or diagnosis.
2. Concurrent conditions and history of other diseases:
 - a. History or clinical manifestations of significant unstable metabolic, hepatic, renal, hematologic, pulmonary, cardiovascular, gastrointestinal, urological, neurological, or psychiatric disorders.
 - b. Clinically significant cardiac disease, including unstable angina, acute myocardial infarction, and or cardiac conduction issues within 180 days of the date of study drug administration.
 - c. Current New York Heart Association Class II to IV congestive heart failure or uncontrolled arrhythmia.
 - d. History of osteomyelitis, PJP, or bronchiectasis.
 - e. Active bacterial, fungal, parasitic, or viral infection that requires antibiotic therapy. Participants with acute infections requiring treatment should delay screening/enrollment until the course of therapy has been completed and the event is considered resolved. Prophylactic antibiotics will be permitted if they have been started at least 28 days before the screening visit.
 - f. History within 6 months before screening, or current presence at screening, of poorly healing wound and/or cutaneous ulcers.
 - g. Prior head or neck irradiation.
 - h. History of or ongoing serious illness or medical, physical, or psychiatric condition(s) that, in the investigator's opinion, would interfere with full participation in the study, including administration of study drug and attending required study visits; pose a significant risk to the participant; or interfere with interpretation of study data.
3. Positive test results for TB from the QuantiFERON-TB Gold test or T-spot.TB test at screening. If a result is indeterminate, the test should be repeated. If the repeat test result is positive, the participant is excluded. If the repeat test result is indeterminate, a purified protein derivative skin test should be done, and if there is < 5 mm of induration, the participant can be enrolled.
4. Positive serology test results for HIV antibody, hepatitis B surface antigen, hepatitis B surface antigen antibody, HBV core antibody, or HCV (HCV antibody with positive HCV-RNA) at screening.
5. Severely impaired liver function (Child-Pugh Class C).

6. Prior or ongoing therapy with:

- a. Any drug that inhibits PI3K (examples of drugs targeting this pathway include but are not limited to leniolisib, seletalisib, INCB040093, idelalisib, and duvelisib) at any time before baseline or during study.
- b. Immunologic or other immunosuppressive therapy, or B-cell targeted therapy (eg, rituximab, other anti-CD20 agents, anti-CD19 agents, anti-CD22 agents, anti-CD52 agents) or LyS-targeted therapy (eg, belimumab, CAML interactor) or other biologic investigational agent (eg, CD40L antibody) or cyclophosphamide within the prior 365 days before baseline or during study.
- c. BTK inhibitors (examples of drugs targeting this pathway include but are not limited to ibrutinib and PCI32765) within 90 days before baseline or during study.
- d. Use of anti-TNF α therapy, IL-1–receptor antagonist, monoclonal antibody to IL-1, costimulation modulator, monoclonal antibody to IL-6 or IL-6–receptor, monoclonal antibody to IL-17, monoclonal antibody to IL-23, JAK inhibitor, IV immunoglobulin, plasmapheresis, or Staph protein A column within 90 days before baseline or during study.
- e. Use of any experimental drug therapy for SS within 90 days before baseline or during study.
- f. Use of nutraceuticals, ayurvedic, herbal, and other nonprescription therapies used for SS are permitted with investigator review, provided the participant has been taking the therapy for at least 60 days as a stable regimen and agrees to continue taking the same preparation at the same dose regimen during the course of the study.
- g. Antimalarials, if ongoing, should be stable within 60 days of baseline and be anticipated to remain stable throughout the 12-week study assessment period.
- h. Glucocorticoids at doses \geq 20 mg prednisone equivalents per day within 60 days before baseline or during study. Administration of glucocorticoids at doses of 20 mg or less must be stable within 30 days of baseline and be anticipated to remain stable throughout the 12-week study assessment period.
 - i. Use of anticholinergics within 30 days before baseline or during study.
 - j. Use of any potent cytochrome CYP3A4 inhibitors or inducers within 14 days or 5 half-lives (whichever is longer) before baseline or anticipated during the study.
 - k. Use of cholinergic agents such as pilocarpine within 12 hours of salivary flow visits at Day 1 and Weeks 4, 8, and 12.
7. Receipt of any live vaccine in the 30 days before screening. NOTE: Participants will not be allowed to receive live or attenuated vaccines during their participation in the study or until 30 days after the last dose of study medication with the exception of influenza vaccine.
8. No major surgery within 30 days before screening. Inadequate recovery from toxicity and/or complications from a major surgery before starting therapy.

9. Current alcohol or drug use that, in the opinion of the investigator, will interfere with the participant's ability to comply with the dose regimen and study evaluations.
10. Laboratory values at screening defined in [Table 6](#).

Table 6: Exclusionary Laboratory Values

Laboratory Parameter	Exclusion Criterion
Hematology	
Platelets	$\leq 100 \times 10^9/\text{L}$
ANC	$\leq 1.5 \times 10^9/\text{L}$
Hepatic	
ALT	$>2 \times \text{ULN}$
AST	$>2 \times \text{ULN}$
Renal	
eGFR	Participants with inadequate renal function defined as eGFR $\leq 50 \text{ mL/min}$

11. Women who are pregnant or breastfeeding.
12. Any condition that would, in the investigator's judgment, interfere with full participation in the study, including administration of study drug/treatment and attending required study visits; pose a significant risk to the participant; or interfere with interpretation of study data.
13. Inability of the participant (or parent, guardian, or legally authorized representative) to comprehend the ICF or unwillingness to sign the ICF.

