2.4.3. Justification for Dose

[REDACTED]

[REDACTED]

[REDACTED]

[figure not shown]
Refer to the INCB050465 [IB](#) for further details.

[REDACTED]

The most prominent findings following repeat-dose exposure to INCB050465 in both rats and dogs were lymphoid depletion, most notably B-cell regions, of multiple lymphoid organs, including lymph nodes, spleen, thymus, and gut-associated lymphoid tissue, at all doses. Lymphoid depletion was considered a DLT. Effects on the lymphoid system are an expected result of immunomodulatory effects of PI3K δ inhibition (Marone et al 2008, Pillai and Cariappa 2009). Reversibility of the effects on the lymphoid system was clearly demonstrated and would be expected to occur in a clinical setting.

INCB050465 was evaluated in 1-month (28 days) and 3-month (91 days) toxicology studies in Sprague Dawley rats and beagle dogs. In the rat studies, INCB050465 was administered daily for 1 month at doses of 10, 30, or 100 mg/kg per day or daily for 3 months at doses of 3, 7.5, or 15 mg/kg per day. In the dog studies, INCB050465 was administered daily for 1 month at doses of 1, 3, or 15 mg/kg per day or daily for 3 months at doses of 0.3, 0.75, or 1.5 mg/kg per day. Recovery was evaluated after a 4-week (1-month study) or 6-week (3-month study) recovery period in both species.

The primary effect observed in 1-month and 3-month studies in both rats and dogs was dose-dependent immunosuppression (evident as minimal to marked depletion of lymphoid tissues, including thymus, lymph nodes, spleen, and gut-associated lymphoid tissue), which was attributed to the pharmacologic activity of INCB050465. All lymphoid effects showed evidence of reversibility at the end of the study recovery periods.

[REDACTED]

[REDACTED]

[REDACTED]

[REDACTED]

The potential risk associated with INCB050465 clinical administration is expected to be low based on the proposed dose of 1 mg, adequate exposure margins, the demonstrated lack of findings in recovery animals following drug withdrawal, and comprehensive evaluation of safety and PK.

For more detailed information about the known and expected risks and reasonably expected AEs of INCB050465, refer to the [IB](#).

[REDACTED]

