6.6.3. Prohibited Medications and Procedures

The following medications and procedures are prohibited during the study from screening through the follow-up visit and before the study as indicated for individual medications:

At any time before baseline (Day 1):

- Any drug that inhibits PI3K (examples of drugs targeting this pathway include but are not limited to leniolisib, seletalisib, INCB040093, idelalisib, and duvelisib).

Within 1 year (365 days) before baseline (Day 1):

- Immunologic or other immunosuppressive therapy, or B-cell targeted therapy (eg rituximab, other anti-CD-19 agents, anti-CD-20 agents, anti-CD-22 agents, anti CD52 agents) or LyS-targeted therapy (eg, belimumab, CAML interactor) or other biologic investigational agent (eg, CD-40L antibody) or cyclophosphamide.
- Anti-TNF α therapy, IL-1-receptor antagonist, monoclonal antibody to IL-1, costimulation modulator, monoclonal antibody to IL-6 or IL-6-receptor, monoclonal antibody to IL-17, monoclonal antibody to IL-23, JAK inhibitor, IV immunoglobulin, plasmapheresis, or Staph protein A column.

Within 3 months (90 days) before baseline (Day 1):

- Any experimental drug therapy for SS.
- BTK inhibitors (examples of drugs targeting this pathway include but are not limited to ibrutinib and PCI32765).

Within 2 months (60 days) before baseline (Day 1):

- Glucocorticoids at doses > 20 mg prednisone equivalents.

Within 1 month (30 days) before baseline (Day 1):

- Anticholinergics.
- Receipt of any live vaccine. Note participants will not be allowed to receive live or attenuated vaccines during their participation in the study or until 30 days after the last dose of study medication with the exception of influenza vaccine.

Within 2 weeks (14 days) before baseline (Day 1):

- Any potent CYP3A4 inhibitors or inducers within 14 days or 5 half-lives (whichever is longer) before the first dose of INCB050465 or anticipated during the study.

Within 12 hours (< 1 day) before baseline (Day 1):

- Cholinergic agents such as pilocarpine.

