9.5. Adverse Events of Special Interest

Adverse events of special interest are defined as occurrences of PJP or other serious infections due to bacterial, mycobacterial, invasive fungal, viral, or other opportunistic pathogens; colitis; and exfoliative dermatitis.

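### The on-study ban on live vaccines exempts influenza vaccine without naming the type, so read literally it permits a live attenuated influenza vaccine during dosing

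*Protocol*

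**What the plan says.** Exclusion 7 in Protocol 5.2 sets a pre-study condition and then an on-study rule. It begins "Receipt of any live vaccine in the 30 days before screening. NOTE: Participants will not be allowed to receive live or attenuated vaccines" and continues "during their participation in the study or until 30 days after the last dose of study medication with the exception of influenza vaccine".

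Protocol 6.6.3 opens its list with "The following medications and procedures are prohibited during the study from screening through the follow-up visit", and adds that individual items also carry their own pre-study windows. Under the heading for the 30 days before Day 1, one bullet reads "Receipt of any live vaccine. Note participants will not be allowed to receive live or attenuated vaccines during their participation in the study" and then extends the rule "until 30 days after the last dose of study medication with the exception of influenza vaccine".

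On the background risk, the nonclinical text under Protocol 2.4.3 reports: "The primary effect observed in 1-month and 3-month studies in both rats and dogs was dose-dependent immunosuppression". The same section says: "The potential risk associated with INCB050465 clinical administration is expected to be low based on the proposed dose of 1 mg". Protocol 9.5 includes among the adverse events of special interest "occurrences of PJP or other serious infections due to bacterial, mycobacterial, invasive fungal, viral, or other opportunistic pathogens". Protocol 5.2 (item 6h) and 6.6.2 allow glucocorticoids at a stable dose.

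**The concern.** A ban on live or attenuated vaccines does not reach inactivated ones. If the sponsor only meant that routine inactivated influenza vaccination may go ahead, no exception was needed. As written, the one influenza product that the exception releases from the ban is a live attenuated one.

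That matters because the study drug suppresses immune function in animals, participants may be on glucocorticoids as well, and the sponsor already treats live vaccines as a hazard and serious viral infection as an event of special interest. The visible text gives no reason why a live influenza virus should be treated differently from any other live vaccine. The question could well come up at a site, since the protocol's own account of current care (2.2) asks that patients' vaccinations be kept current.

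**Working it through.** No arithmetic applies. The check is a comparison of the two rules, followed by a check of what else in the plan bears on them.

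1. **Scope of the ban.** Both notes cover live or attenuated vaccines, during participation and until 30 days after the last dose. Inactivated vaccines are not named in either.

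2. **Scope of the exception.** Both notes exempt influenza vaccine, with no type stated. I assume that influenza vaccine exists in inactivated and live attenuated forms; the documents do not discuss products.
   - Inactivated form: outside the ban, so the exception changes nothing.
   - Live attenuated form: inside the ban, so the exception releases it.

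   The exception therefore has a practical effect only for the live form.

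3. **Agreement between sections.** In 6.6.3, the sentence on any live vaccine and the note with the exception stand in one bullet. The note in 5.2 gives the same on-study rule and the same exception in matching words. The two sections give one rule.

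4. **Pre-study and on-study periods.** The first sentence of exclusion 7 has no influenza exception, so a live influenza vaccine in the 30 days before screening excludes a person, while the note would allow it once the person is on study. These are different periods, so the rules do not conflict. It is odd, though, for protection to be looser during exposure than before it.

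5. **Safeguards.** Protocol 6.6 counts vaccines among the treatments to be recorded in the eCRF and directs questions about concomitant therapy to the medical monitor. Protocol 9.3 has the investigator weigh concomitant therapy and timing when judging causality. Under SAP 8.2.1, adverse events count as treatment-emergent unless clearly not so, so an infection after vaccination would appear in the all-cause tables and could be reviewed case by case.

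6. **Effect on the plan's figures.** None. The only sample-size figure is the chance above 90% of seeing at least one event of interest in 12 participants at a 20% rate. It reproduces as 1 − 0.8^12 = 0.931 and does not depend on the vaccine wording.

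**The case against.** A reader might infer that the protocol contradicts itself: the 6.6.3 lead-in and the first sentence of the bullet forbid any live vaccine from screening onward, while the notes allow an influenza one, so two sites could follow two different rules. The documents do not support that. The note is part of the same bullet on the prohibited list, and a general ban followed at once by a specific exception is ordinarily read as one rule. A site consulting either section meets the same exception. A conflict appears only if the lead-in is applied to the first sentence and the attached note is ignored.

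The strongest remaining defence has three parts. First, the exception may be deliberate: some risk text is redacted, and the Investigator's Brochure, to which the protocol refers for details of risk, is not available here. Second, a site in doubt has a stated route to the medical monitor before vaccinating. Third, the study is small and short (12 participants, 12 weeks), the protocol expects low risk at 1 mg, and it reports that the lymphoid effects in animals were reversible.

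All three stand as limits on the size of the point. None removes it. If the exception is deliberate, the visible text should name the live product and say why it is acceptable. If it is loose wording, it permits something the sponsor did not intend. The route to the medical monitor helps only a site that sees a question to ask, and wording that appears to grant permission may not prompt one.

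**Conclusion.** The exception is over-broad. Read literally, two notes that agree with each other permit a live attenuated influenza vaccine during treatment with a drug whose main effect in animals was immunosuppression. This is a minor, safety-relevant wording fault that is worth correcting.

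Its size cannot be put as a number: the documents give no rate for use of live influenza vaccine or for infection after it. Harm is conditional on a live product being chosen without consulting the medical monitor and on an infection following. No endpoint, estimate, sample size or analysis changes.

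The conclusion rests on reading live or attenuated in its plain sense, so that inactivated vaccines are outside the ban, and on the assumption that a live attenuated influenza product could be available to a site. It does not rest on any view of the sponsor's intent, which the documents do not show.

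**What to change.** In both notes (Protocol 5.2 exclusion 7 and 6.6.3), replace the exception with two plain statements, for example: *Live or attenuated vaccines, live attenuated influenza vaccine included, may not be given while a participant is in the study or in the 30 days following the final dose. Inactivated influenza vaccine is permitted.* This is clearer than adding the word inactivated to the present exception, which would then exempt a product that the ban never covered.

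If the sponsor does mean to allow the live product, both places should name it and give the reason.

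The cost is one sentence in each of two sections. Visits, sample size and analysis stay as they are.

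The same edit could settle a separate small mismatch: the pre-study live-vaccine window is counted back 30 days from screening in 5.2 but from Day 1 in 6.6.3.

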5.3. Lifestyle Considerations

No restrictions are required.

5.3.1. Meals and Dietary Restrictions

Not applicable.

5.4. Screen Failures

Screen failures are defined as participants who consent to participate in the clinical study but are not subsequently entered in the study.

Tests with results that fail eligibility requirements may be repeated once during screening if the investigator believes the result to be not consistent with the participant's clinical status. Additionally, a participant who fails screening may repeat the screening process 1 time if the investigator believes that there has been a change in eligibility status. Participants who rescreen must reconsent and be assigned a new participant number.

